Data Analysis: Data management and analysis will be supervised by [name] (Biostatistician and consultant). Data will be analyzed from all randomized subjects on whom we have a baseline assessment and at least one post-baseline evaluation. Every attempt will be made to obtain at least one follow up assessment on any individuals who drop out of treatment. Data will be screened for outliers, missing values, and violation of statistical assumptions. Preliminary analyses will be used to examine the descriptive statistics of the study sample and assess for the influence of outliers and non-normally distributed variables for possible exclusion or transformation. Gender, age, medications, depression, and TBI-related variables will be examined for differences between groups at baseline; they will be added as covariates if differences are significant.

Missing Data: Missing data values will be minimized by intensive training of the staff in techniques of clarifying answers and checking questionnaires while Veterans are on-site. When missing values are identified, several approaches to acquire the necessary data will be employed including 1) contacting the Veterans to obtain the missing data and/or 2) examining the missing data to assess randomness. We expect missing data to be randomly distributed. Missing data (i.e., loss to follow up) will be tested to determine if it is informative, and the methods developed by Diggle (1989) and Ridout (1991) to test for completely random dropouts will be applied. We will test whether the drop-outs are random or systematic by comparing the drop-outs with the study completers on the baseline data. An absence of significant differences would support the random nature of drop-outs. If the extent of missing data is small and the data appear to be consistent with a missing-at-random model (MAR), then the maximum-likelihood analysis using all randomized cases and the observed data is an appropriate method for handling the missing data.

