Analyses will be conducted using multilevel modeling (MLM; also known as hierarchical linear modeling and linear mixed effects modeling). MLM has several advantages over more traditional analytic approaches such as change scores or repeated measures ANOVAs, as it allows for the inclusion of participants who have missing data and who dropped out of the study prematurely without using data imputation or biased procedures that often reduce power, such as casewise deletion. MLM also accounts for the fact that repeated observations across time are not independent but are nested within individuals. This method can provide an estimate of the individual variability around the population trend, the variability of the individual intercepts (baseline symptom levels) and slopes (change in symptoms across time), and the correlation between them. Initial model testing will be conducted to determine whether including individual-level random effects of intercept and slope (to model variability in initial symptom level and variability in response to treatment) will improve model fit. In addition to including the significant random effects, the model will include the fixed effects of treatment group, time, and group-by-time interaction. Data will be analyzed from all randomized subjects (full intent-to-treat sample) using all available data collected at the different assessment points.

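### A non-significant baseline comparison is taken as support for random drop-out, and no analysis of departures from missing at random is planned

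*Combined protocol and SAP*

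**What the plan says.** The Missing Data paragraph of Section 9 starts from an expectation: "We expect missing data to be randomly distributed". It plans two checks. Published methods "to test for completely random dropouts will be applied", and drop-outs are compared with completers on baseline data. The second check is read as follows: "An absence of significant differences would support the random nature of drop-outs". The paragraph then sets a condition: "If the extent of missing data is small and the data appear to be consistent with a missing-at-random model (MAR), then the maximum-likelihood analysis" is called appropriate. It does not define small, and it does not say what happens if the condition fails.

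The Data Analysis paragraph just before it defines the analysis set: "Data will be analyzed from all randomized subjects on whom we have a baseline assessment and at least one post-baseline evaluation". It adds: "Every attempt will be made to obtain at least one follow up assessment on any individuals who drop out of treatment". The multilevel modelling paragraph that follows defines the set differently: "Data will be analyzed from all randomized subjects (full intent-to-treat sample) using all available data collected at the different assessment points". It adopts the mixed model without any condition.

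Elsewhere, Hypothesis 2b in Section 6 predicts a higher rate of treatment completion with CEFT-CPT than with control. Section 15 allows investigators to withdraw participants from the study for non-compliance with treatment or a new psychiatric or medical problem. Section 14 provides for withdrawal, if necessary, when an acute psychiatric issue arises.

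**The concern.** A non-significant test does not show that there is no difference, least of all with a few dozen drop-outs. A baseline comparison also addresses the wrong question. The mixed model does not need drop-out to be unrelated to baseline. It needs drop-out to be unrelated to the unseen outcomes, given what was observed. Baseline data cannot show that. Nor can tests of completely random drop-out, because they too use only observed data.

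The documents give grounds for caution about random missingness. Withdrawal for non-compliance or for clinical reasons can tie a missing post-CPT score to how therapy was going. If retention also differs by arm, even the same departure from MAR in both arms leaves a bias in the group difference.

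What is at stake is how the Hypothesis 2a result can be read. Under the plan, a passed check could be reported as support for the MAR analysis. Nothing planned would show how far drop-outs must depart from MAR before the conclusion changes, or in which direction they would have to depart.

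**Working it through.** The documents available for review state no loss-to-follow-up rate, effect size, SD or power, so there is no figure of the plan's own to reproduce on this point.

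**1. Power of the baseline comparison.**

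Inputs: 150 randomised, 75 per condition (Section 9, Subject recruitment; Section 10). The number of drop-outs is assumed to be 30 to 75, that is 20% to 50%. A two-sided 5% t-test is also assumed.

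Formula: noncentral t with noncentrality d × √(n₁n₂/(n₁+n₂)) and n₁+n₂−2 = 148 degrees of freedom. For 30 drop-outs, n₁n₂/(n₁+n₂) = 30×120/150 = 24. At d = 0.3 the noncentrality is 0.3×√24 = 1.47 and power is 31%.

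| Drop-outs / completers | Noncentrality at d = 0.3 | Power at d = 0.3 | d needed for 80% power |
|---|---|---|---|
| 30 / 120 | 1.47 | 31% | 0.58 |
| 45 / 105 | 1.68 | 39% | 0.50 |
| 60 / 90 | 1.80 | 43% | 0.47 |
| 75 / 75 | 1.84 | 45% | 0.46 |

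A 0.3 SD baseline difference would therefore be missed more often than found at every drop-out level shown.

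**2. What the checks can see.**

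Suppose the outcome is recorded only at the three full assessments, and drop-out depends solely on a person's own change during CPT. Suppose also that this change is unrelated to the scores before CPT. The baseline and post-training scores then carry no information about the drop-out mechanism. A check built on them rejects at about its nominal rate, as it would with truly random drop-out, so passing it says nothing about this mechanism.

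**3. Size and direction of bias if drop-outs depart from MAR.**

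Write δ for the number of points by which drop-outs end worse than MAR predicts (a higher score is worse), and r for retention at the post-CPT assessment. Express the group difference as CEFT minus control, so that a negative value favours CEFT. Then:

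true difference − MAR estimate = δ_CEFT × (1 − r_CEFT) − δ_control × (1 − r_control)

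Assumed inputs: δ = 5 where it applies; control retention 50%; CEFT retention 65% or 75%.

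| Who is worse than MAR predicts | r_CEFT = 65% | r_CEFT = 75% | MAR estimate is biased |
|---|---|---|---|
| Both arms | 5×0.35 − 5×0.50 = −0.75 | 5×0.25 − 5×0.50 = −1.25 | against CEFT |
| CEFT drop-outs only | 5×0.35 = +1.75 | 5×0.25 = +1.25 | in favour of CEFT |
| Control drop-outs only | −5×0.50 = −2.50 | −5×0.50 = −2.50 | against CEFT |

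The sign depends on which arm departs from MAR, so the sensitivity analysis has to let δ differ by arm.

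**4. The two analysis sets.**

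One statement requires a post-baseline evaluation; the other takes everyone randomised. A participant seen only at baseline is excluded by the first and included by the second. Someone who attends the post-training visit and then leaves CPT is in both sets, with no post-CPT outcome required. The one-evaluation rule therefore does not secure the outcome on which the treatment comparison after CPT depends.

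**The case against.** Four points on the other side have force.

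- **Leaving therapy is not the same as a missing outcome.** The plan promises efforts to follow up drop-outs, pays $70 for the post-therapy assessment (Section 9, Financial Incentives), and requests a final meeting to assess clinical status when someone leaves early (Section 15). These reduce the risk. They do not remove it: the follow-up promise does not name the post-CPT assessment, and Section 15 does not say that outcome instruments are given at the final meeting.
- **Unequal completion is compatible with MAR**, because arm is in the model: "the model will include the fixed effects of treatment group, time, and group-by-time interaction". This is right. Hypothesis 2b alone does not show that MAR fails.
- **Symptoms are measured weekly during CPT** (Section 9, Design and methods), with the PCL-5 given at therapy sessions. If these scores enter the drop-out tests and the model, they give some chance of detecting drop-out driven by poor response, and they reduce the bias. The argument in step 2 of the working therefore applies fully only to an outcome seen at the three visits, such as the CAPS-5.
- **The mixed model is already adopted without condition** in the multilevel modelling paragraph. It is a sound main analysis and should stay. What remains is the conditional wording in the Missing Data paragraph.

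A reader might infer two stronger things. One is that the planned checks would pass in nearly every trial whatever the cause of drop-out. That follows only when drop-out is assumed independent of every score tested, and it ignores the weekly scores, so it is not a property of the plan. The other is that the flaw would manufacture a positive Hypothesis 2a result. The documents do not support that either: with more control drop-out and drop-outs worse in both arms, the bias runs against CEFT.

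**Conclusion.** The point holds. The stated inference is invalid, and the plan has no analysis of departures from MAR and no course of action if missingness is not small. The power figures rest on the planned 150 randomised and an assumed 30 to 75 drop-outs.

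The bias figures, from 2.5 points against CEFT to 1.75 points in its favour, rest on an assumed 5-point departure and assumed retention. They are not forecasts. The roughly 50% given in Section 7 combines drop-out, non-response and relapse, so it is not a retention figure. The documents do not establish that MAR fails, or which way any bias would run. The gap is that nothing planned would show how much this matters.

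The two definitions of the analysis set conflict and need reconciling. The numerical effect is probably small, because baseline-only participants carry little information about the group-by-time interaction. This should be changed, but it does not undermine the main model.

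**What to change.** 1. Delete the sentence "An absence of significant differences would support the random nature of drop-outs". Report the drop-out comparison and the tests of random drop-out by arm, as description only.
2. State that the mixed model of the multilevel modelling paragraph is the Hypothesis 2a analysis whatever these checks show. Remove the condition that missingness be small and look MAR. Reconcile the two analysis sets to all randomised subjects, which suits a likelihood model on available data.
3. Add one sensitivity analysis: a delta-adjusted tipping point for the post-CPT group difference, with separate shifts for CEFT and control drop-outs. Use the trial's own standard error, and report the direction of each shift as well as its size.

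The cost is plan wording and a little programming. No visit, participant or measure is added, and no change to any withdrawal rule is proposed.

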6) Provide a statement of specific aims and hypotheses that serve as the basis for this protocol. Emphasize those aspects that justify the use of human subjects.

Aim 1: Investigate whether Computerized Executive Function Training (CEFT) leads to objective and subjective improvements in executive functioning and whether this in turn mediates PTSD symptom improvement.

Hypothesis 1a: CEFT will be associated with improvements in both objective and subjective executive functioning.

Hypothesis 1b: Enhanced executive functioning will mediate the relationship between treatment group and PTSD symptom improvement.

Aim 2: Investigate the efficacy of administering CEFT prior to Cognitive Processing Therapy (CEFT-CPT) in improving treatment adherence, completion rates, and outcomes in OEF/OIF Veterans with PTSD.

Hypothesis 2a: Individuals in the CEFT-CPT condition will have greater improvements in PTSD symptoms and quality of life than the control condition (placebo word training plus CPT).

Hypothesis 2b: Individuals in the CEFT-CPT condition will have higher rates of treatment engagement (i.e., completing more hours of homework and attending a greater number of sessions) and higher rates of treatment completion than those in the control condition.

Aim 3: Investigate whether functioning of brain regions in an EF network at baseline predicts treatment response.

Hypothesis 3: Dysfunction in a network of brain regions supporting EF will predict poorer response to treatment. Specifically, those who do not complete treatment and who demonstrate a poorer response will exhibit decreased connectivity between dorsolateral PFC and other regions, including anterior cingulate cortex and parietal cortex, compared to completers and better responders.

Section 7 - Background and Significance

7) Provide a succinct discussion of relevant background information to justify performing the proposed study.

PTSD affects approximately 14% of OEF/OIF Veterans and leads to considerable personal and societal costs (e.g., increased morbidity, reduced work productivity, poorer relationships). Cognitive behavioral therapy (CBT) has been shown to be one of the most effective treatments for PTSD. The Institute of Medicine

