- **Client Satisfaction with Treatment:** Client Satisfaction Questionnaire (CSQ; Attikisson & Zwick, 1982) is an 8-item self-report scale measuring satisfaction with treatment. It has excellent internal consistency and correlates with therapists' estimates of client satisfaction. This instrument will be used to measure participants' satisfaction with the interventions.
- **Homework Compliance:** Homework Compliance Scale (HCS; Primakoff et al., 1986) is a single item questionnaire in which participants rate their degree of homework compliance on a scale from 0 (homework was not assigned) to 6 (I did more of the assigned homework than requested). An estimate of the number of minutes spent completing homework since the previous session and number of completed worksheets and assignments will also be recorded at each CPT session.
- **Alcohol Screening Tool:** The Alcohol Use Disorders Identification Test-C (Audit-C; Saunder et al., 1993) is a 3-item screening measure used to screen for alcohol use disorder, which is an exclusion criteria for the study.

Neuroimaging: Collected only at baseline

Experimental fMRI Tasks:

N-Back Working Memory Task: In this task, pseudo-words are presented on each trial and the participant must determine whether the current stimulus matches the one n-back. There are 3 types of n-backs in the task: 1-back, 2-back, and 3-back. Participants respond via a keystroke whenever they see a pseudo-word repeated either one, two, or three pseudo-words back. Each participant will receive a practice block before going into the scanner and two blocks while in the scanner, with each block containing all 3 N-back conditions in an alternating order. Reaction time and accuracy on each trial are recorded during scanning.

Go-No Go Inhibition Task: In this task, shapes are presented on screen. Participants are instructed to make a button press to every shape except when a circle or square appears on screen. Each participant will receive a practice block before going into the scanner and two blocks while in the scanner. Reaction time and accuracy on each trial are recorded during scanning.

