2. Auditory Ace: auditory working memory exercise, essentially an N back task where auditory information is retained and manipulated to determine if the current card matches a card N steps back in the sequence
3. Card Shark: visuospatial working memory exercise, similar to the Auditory Ace, except the information used to determine matches is presented visually
4. Juggle Factory: visuospatial working memory exercise, participants reconstruct a sequence of numbers in moving circles in the correct order, at more difficult levels participants must inhibit the influence of distractors
5. Mixed Signals: inhibition exercise, participants respond if what they hear and see matches in a particular way (while ignoring irrelevant information), otherwise they withhold their response
6. Divided Attention: inhibition exercise, participants indicate whether two objects match on a particular aspect (e.g., shape, color, fill) while ignoring irrelevant/competing aspects

Placebo word games: Participants in the active control group will be assigned to complete computerized placebo game training at the same frequency as CEFT. *Games and puzzles will be accessed online via BrainHQ in a similar manner to the CEFT condition.* This placebo condition controls for the effects of computer exposure, contact with research staff, and monetary payments. In addition, it controls for nonspecific engagement and motivation through the reinforcement of graphics-based computer games but does not provide the constrained, intensive, adaptive training of specific executive functions that the active condition provides. Participants will rotate through a series of games (e.g., *sudoku*, *crossword*, *connect four*) for the same number of hours as the EF training condition. After 6 weeks of game training, they will also receive CPT-C as detailed below.

Cognitive Processing Therapy: CPT is an evidence-based, trauma-focused therapy for PTSD endorsed by the VA/DoD Practice Guidelines and is widely available within VASDHS. Patients will receive a well-validated version of CPT, CPT-Cognitive only (CPT-C), which is a standard PTSD treatment provided at the VA that differs from the original version of CPT in that it does not include written trauma accounts. It entails 12 visits to the VA, each lasting 50 minutes.

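### The stated mixed model cannot be fitted to two of the three H2b outcomes (completion and sessions attended), and one of two conflicting analysis-set rules could drop non-completers

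*Combined protocol and SAP*

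**What the plan says.** Hypothesis 2b (Section 6, Aim 2) predicts that the CEFT-CPT arm will show "higher rates of treatment engagement (i.e., completing more hours of homework and attending a greater number of sessions) and higher rates of treatment completion". That makes three outcomes: homework, sessions attended and completion.

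Section 9, Data Analysis, gives one model for the clinical outcomes: "Analyses will be conducted using multilevel modeling", which it equates with a linear mixed model. Its fixed part is set out: "the model will include the fixed effects of treatment group, time, and group-by-time interaction". Random effects are added if they improve fit, and they are explained in terms of symptom scores: "the variability of the individual intercepts (baseline symptom levels) and slopes (change in symptoms across time". The only other model named is a general linear model under Image processing, which is for the fMRI data.

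The three H2b outcomes differ in structure:

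- **Homework.** Minutes spent and worksheets completed "will also be recorded at each CPT session" (Assessment Measures, Homework Compliance).
- **Sessions attended.** Of CPT-C the protocol says: "It entails 12 visits to the VA, each lasting 50 minutes". The outcome is therefore one total per person, from 0 to 12.
- **Completion.** One yes or no per person. The available text does not define it.

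The analysis set is stated twice. The opening paragraph of Data Analysis requires a baseline assessment and at least one later evaluation. The paragraph on multilevel modelling says all randomised participants, as full intent-to-treat.

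**The concern.** A group-by-time model tests whether the arms change differently over repeated measurements. Completion and total attendance have no baseline value and no repeats, so the model has nothing to work on. H2b is one of the two hypotheses of Aim 2. If the plan names no test for two of its three outcomes, the choice between a comparison of proportions, means, ranks or counts is left open until the data are in hand.

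The analysis set matters more here than for symptom scores. For completion, leaving early is the outcome itself. A rule that removes people because they left early removes failures from the denominator.

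**Working it through.** The plan states no completion rate and no calculation for H2b, so there is no figure of its own to reproduce. The check covers whether the model can be estimated, and what the two analysis sets imply.

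**Inputs from the protocol:** about 150 randomised, 75 per condition; fixed effects for group, time and group-by-time; three main assessments; 12 CPT sessions; homework recorded per session.

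**1. One value per person (completion, total sessions).** The fixed-effect columns are [1, G, T, G×T]. All values sit at one time point, so T is a constant c. Then T = c×1 and G×T = c×G. Two of the four columns repeat the other two, so the rank is 2 of 4. A numerical check with 75 per arm gives rank 2, and a trial fit on simulated data stops with a singular matrix.

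**2. Dropping time does not rescue the stated model.** With y = b0 + b1·G + u + e and one value per person, only the sum Var(u) + Var(e) is identified. The trial fit returns a Hessian that is not positive definite. What remains is an ordinary two-group regression, which the plan does not state.

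**3. Repeated records.** With 3 assessments the same columns have rank 4. With 12 session-level records they also have rank 4, and a random-intercept model fitted to simulated homework data converged. Homework can therefore be analysed as stated. There is no pre-CPT homework value, so the plan still has to say whether the group effect or the group-by-time effect is the test.

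**4. Effect of the post-baseline rule on completion.** Let p be the true completion rate and L the share of non-completers with no post-baseline evaluation, with every completer retained:

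observed rate = p / [p + (1 − p)(1 − L)]

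The documents give neither p nor L. Assuming p = 50% in control and 65% in CEFT-CPT:

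| L, both arms | Control | CEFT-CPT | Difference |
|---|---|---|---|
| 0% | 50% | 65% | 15 points |
| 20% | 50/90 = 55.6% | 65/93 = 69.9% | about 14 |
| 40% | 50/80 = 62.5% | 65/86 = 75.6% | about 13 |
| 60% | 50/70 = 71.4% | 65/79 = 82.3% | about 11 |

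Equal loss inflates both rates but leaves the odds ratio at (65/35)/(50/50) = 1.86. Unequal loss multiplies it by (1 − L control)/(1 − L CEFT-CPT). With 40% lost in control and 20% in CEFT-CPT, it becomes 1.86 × 0.6/0.8 = 1.39.

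**The case against.** The best defence is that the model paragraph is about symptom trajectories and was never meant for completion or attendance. That is a fair reading. On it, the plan is silent on these two outcomes instead of assigning them a wrong model, but the practical result is the same: no test is named.

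Data Analysis also promises screening for non-normality and violated assumptions. The remedies offered are exclusion or transformation. Neither gives a single yes/no value a time axis, and excluding low attendance as outlying would remove the drop-outs. Attendance could be recast as yes/no at each of 12 sessions, but that needs a generalised mixed model, and the plan specifies a linear one.

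On the analysis set, the protocol says every attempt will be made to obtain a follow-up from drop-outs, and it measures symptoms midway through training and weekly during CPT. If those measurements count as evaluations, only people who leave very early are lost. That stands, and it makes the size of the distortion unknown.

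A reader might infer three stronger points that the documents do not support:

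- **That H2b cannot be tested at all.** Per-session homework fits the stated model.
- **That a Gaussian comparison of sessions would waste power on the distribution the trial expects.** The plan never proposes that comparison and gives no session distribution, and the ranking of tests reverses with the distribution assumed for non-completers. The figure of about 50% in Section 7 combines drop-out, non-response and relapse, so it is not a completion rate.
- **That completion should lead H2b.** Nothing in the documents ranks the three outcomes.

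**Conclusion.** The concern holds for two of the three H2b outcomes. The only model stated for clinical outcomes cannot be fitted to completion or total sessions attended (rank 2 of 4), and the available text names no alternative. This follows from the data structure and needs no assumed rates.

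The two analysis-set statements conflict, and the narrower one could overstate completion. The illustration of 50% and 65% appearing as about 63% and 76% assumes those true rates, 40% of non-completers lost in each arm and every completer retained. It shows direction and scale and is not a forecast.

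**What to change.** For H2b, state that all randomised participants are analysed, and remove the requirement for a post-baseline evaluation for these outcomes. Then specify:

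- **Completion:** define it in advance. Use logistic regression on arm and gender (the stratification factor), counting anyone who never starts CPT as not completed.
- **Sessions attended (0 to 12, zero if never started):** name a between-arm model suited to a bounded count, such as proportional odds, adjusted for gender. Other suitable models exist; what matters is naming one in advance.
- **Homework:** keep the multilevel model on the per-session records and state whether the group or the group-by-time contrast tests H2b.

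The cost is SAP wording and a little analysis work. No new data collection should be needed: Section 9.1 has CPT delivered by study staff, so attendance should already be recorded for everyone randomised. The team should confirm this.
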